8.2.4. Non-Parametric Analyses

8.2.4.1. Ranking

For the primary analysis of 6MWT, subjects will be ranked as follows ordered from worst to best:

1. Subjects who died prior to EEOS where time to death is used to rank earlier deaths worse than later deaths,
2. Subjects who are missing EEOS and vital status is unknown at EEOS will be ranked according to time on study drug from worst (shortest time) to best (longest time)
3. Subjects who are missing EEOS because the subject physically cannot perform the test, due to physical incapacity or other reason will be ranked according to time on study drug from worst (shortest time) to best (longest time)
4. Subjects who are missing EEOS and are known to be alive will be ranked according to time on study drug from worst (shortest time) to best (longest time)
5. Completed subject’s values will be ranked from worst (lowest distance) to best (highest distance) performance

Sensitivity analyses of the ranking will be performed by

- a) Only including ranks 1 and 5 above, and for missing reasons besides death, duration on study will be used to rank with shorter duration worse than longer duration
- b) Only including ranks 1, 3, and 5 above, and duration on study will be used to rank subjects who did not die and who are physically able to perform the test with shorter duration worse than longer duration
- c) Imputing subjects who died and who are physically not able to perform the test as zero distance in meters first, then imputing ranks for missing data using ranks 2, 4, and 5 above
- d) Imputing subjects who died or who are physically not able to perform the test (due to physical incapacity, hospitalization, or other reason) as zero distance in meters first, then imputing other missing values as the median of the observed placebo subjects at

the specified visit, then ranking all values from worst (lowest distance) to best (highest distance) performance.

The ranking paradigm with 5 levels and the ranking paradigms a and c above will also be used as sensitivity analyses for the SF-36v2 PCS score key secondary endpoint analyses.

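### SAP 8.2.4.1 sensitivity ranking (c), read literally, places deaths above living subjects with a missing 12-month test; this weakens a death imbalance and reverses it only in offsetting patterns

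*SAP*

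**What the plan says.** SAP 8.2.4.1 ranks subjects for the primary 6MWT analysis in five levels, worst to best:

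- Level 1: "Subjects who died prior to EEOS where time to death is used to rank earlier deaths worse than later deaths".
- Level 2: "Subjects who are missing EEOS and vital status is unknown at EEOS will be ranked according to time on study drug".
- Level 3: subjects physically unable to do the test, also ordered by time on drug.
- Level 4: "Subjects who are missing EEOS and are known to be alive will be ranked according to time on study drug".
- Level 5: "Completed subject’s values will be ranked from worst (lowest distance) to best (highest distance) performance".

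Only level 5 is ordered by a distance.

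Sensitivity ranking (c) has two steps. The first is "Imputing subjects who died and who are physically not able to perform the test as zero distance in meters first"; the second is "then imputing ranks for missing data using ranks 2, 4, and 5 above". Levels 1 and 3 drop out, and no level is named for the zeros. Ranking (d) uses the same zero step, but it also gives every other missing subject a distance (a placebo median) and ends with "then ranking all values from worst (lowest distance) to best (highest distance) performance".

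The section closes by saying that the five-level ranking and "ranking paradigms a and c above will also be used as sensitivity analyses for the SF-36v2 PCS score". Under SAP 8.8.2 the 6MWT variable analysed is change from baseline, by rank ANCOVA, with a van Elteren test as the fallback.

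**The concern.** Ranking (c) mixes two scales. Levels 2 and 4 are ordered by time on drug and sit below level 5. The zeros are distances, and only level 5 handles distances. A programmer who follows the sentence puts each death and each physically unable subject at the bottom of level 5, above every subject in levels 2 and 4. A death then counts as a better outcome than being alive with a missing test, the opposite of the primary order.

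Level 4 is unlikely to be empty. Under Protocol 4.3, subjects who stop drug early have no EOS visit, and their last scheduled visit is Month 12-Day 1. SAP 4.6 (Table 3) targets that visit at day 308 and opens the EEOS window at day 320. Even at the +5-day limit, 308 + 5 = 313 falls short. Unless a further visit lands in the window, these subjects miss EEOS, and the vital-status calls will show many of them to be alive.

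At stake is whether one planned sensitivity analysis for two key secondary endpoints handles death sensibly, and whether two programmers would produce the same result.

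**Working it through.** **Inputs.** The SAP gives no figure for this ranking. The plan supplies only 65 per arm (up to 130 randomised 1:1, SAP 2.2.5). The power statement in SAP 3 reproduces at that size. With p̄ = 0.3625, power = Φ{[0.275 − 1.96√(2 × 0.3625 × 0.6375/65)] / √[(0.25 + 0.174375)/65]} = Φ(0.1097/0.0808) = Φ(1.36) = 91.3%, against 91% stated. All death and missing counts below are assumptions; the documents give none.

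**Position of each group, worst = 1st**

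| Group | Primary | (c) literal | (c) with zeros lowest |
|---|---|---|---|
| Died | 1st | 3rd, tied | 1st, tied |
| Vital status unknown | 2nd | 1st | 2nd |
| Physically unable | 3rd | 3rd, tied | 1st, tied |
| Missing, known alive | 4th | 2nd | 3rd |
| Completers | 5th | 4th | 4th |

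Example: take 130 subjects with 10 deaths and 13 in levels 2 and 4. Under the primary ranking the deaths hold ranks 1–10 (mean 5.5). Under literal (c) they hold ranks 14–23 (mean 18.5), and completers start at rank 24. Deaths pass all 13 missing subjects and no completer.

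**Effect on the comparison.** Let arm A have d_A deaths and m_A living-missing subjects, and likewise arm B. Let K = d + m and n = 65. Assume identical completer distributions and no arm difference in order within the death and missing levels. Let U count the A–B pairs in which A ranks higher, ties as one half, and let X = d_A·m_B − d_B·m_A. Counting pairs gives:

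- Primary: U − n²/2 = ½[n(K_B − K_A) − X]
- Literal (c): U − n²/2 = ½[n(K_B − K_A) + X]

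The tie-corrected variance is (n²/12)[(2n + 1) − Σ(t³ − t)/(2n(2n − 1))], an SD of 214 to 215 in each row below.

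| Deaths A v B | Living-missing A v B | n(K_B − K_A) | X | z primary | z literal (c) |
|---|---|---|---|---|---|
| 12 v 4 | 10 v 10 | 65 × (14 − 22) = −520 | 120 − 40 = 80 | −300/214.2 = −1.40 | −220/214.2 = −1.03 |
| 8 v 2 | 10 v 10 | −390 | 80 − 20 = 60 | −225/214.3 = −1.05 | −165/214.3 = −0.77 |
| 8 v 2 | 4 v 8 | −130 | 64 − 8 = 56 | −93/214.6 = −0.43 | −37/214.6 = −0.17 |
| 8 v 2 | 2 v 8 | 0 | 64 − 4 = 60 | −30/214.6 = −0.14 | +0.14 |
| 12 v 4 | 2 v 10 | 0 | 120 − 8 = 112 | −56/214.5 = −0.26 | +56/214.5 = +0.26 |

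Simulated trials with the last row's counts gave mean z of −0.30 to −0.23 (primary) and +0.22 to +0.29 (literal).

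**When the sign can change.** With m living-missing in each arm and D extra deaths in A, literal (c) gives −½D(n − m). Since m < n, this is never positive. The sign changes only if X exceeds 65 times the absolute difference in total non-completers, that is, when the death excess in one arm is nearly matched by a living-missing excess in the other.

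**With zeros lowest.** U equals the primary value in every row. If physically unable subjects are present (deaths 6 v 3, unable 2 v 2, unknown 1 v 1, alive-missing 4 v 4), z is −0.50 primary, −0.42 literal and −0.49 with zeros lowest.

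**The case against.** The SAP never says that the zeros belong to level 5. That level is for completers, and a dead subject is not one. In (d) the same zero step leads to the bottom of the scale, so an author may have meant the same in (c). This stands in part: the placement is the literal consequence of the text, not a stated intention. But (d) works only because every missing subject there receives a distance. In (c) they do not, and no position other than level 5 is offered.

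A reader might go further and infer that (c) makes a death imbalance count in the wrong direction, or rewards the arm with more deaths. The documents do not support that as a general claim. Zeros still rank below every walked distance, so the penalty shrinks and normally keeps its sign. Where the sign changes, both values are close to zero.

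Nor is a confirmatory result at risk. The testing sequence in SAP 8.6 does not depend on (c). Rankings (a) and (b) keep deaths lowest, (d) puts them at 0 m on one distance scale, and for PCS SAP 8.2.3.1 separately imputes deaths as the worst value, with a zero-score variant. An odd result from (c) would show up against these.

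The arithmetic above is an unstratified Wilcoxon, not the planned rank ANCOVA. It shows direction and rough size only.

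**Conclusion.** The point holds as a defect in one planned sensitivity analysis. Followed literally, (c) ranks deaths and physically unable subjects above living subjects with a missing EEOS test. A death imbalance is then weakened: z goes from −1.40 to −1.03 with 12 vs 4 deaths and 10 living-missing per arm. It changes sign only in offsetting patterns (−0.26 to +0.26 with 12/2 vs 4/10). These sizes rest on assumed counts, identical completers and 65 per arm. The primary 6MWT analysis is unaffected.

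Two related gaps belong with it. If change from baseline is what gets ranked, 0 m becomes minus the baseline distance. With entry distances between 100 m and 600 m, a death from a 110 m baseline (−110 m) would rank above a completer who fell from 500 m to 350 m (−150 m). For SF-36v2 PCS, a distance of zero is undefined. The correction is worth making before unblinding.

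**What to change.** Reword (c) for 6MWT: subjects who died or are physically unable take the lowest tied rank, below level 2; then come level 2, level 4, and level 5 with observed values only. State that this applies to the ranks used in the change-from-baseline analysis, so that 0 m is not converted to minus baseline.

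For SF-36v2 PCS, replace the zero distance with the lowest tied rank for deaths. Rank all other subjects missing EEOS under level 2 (vital status unknown) or level 4 (known alive). Physical inability to walk then needs no separate rule there.

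The cost is one or two sentences of SAP text and one programming rule. The downside is that deaths are tied in (c), so time to death is not used there; a common 0 m value already has that effect.

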8.2.5. Last Observation Carried Forward (LOCF)

As sensitivity analyses for changes from baseline in SF-36v2 PCS score, SF-36v2 MCS score, SF-36v2 subscales, and NIS-LL total and component scores, subjects who missed a scheduled visit will also have their missing visit values imputed using LOCF. For LOCF, each subject's last non-missing observation will be carried forward to the missing visit observation.

8.2.6. Complete Case Analysis

As sensitivity analyses for changes from baseline in SF-36v2 PCS score, SF-36v2 MCS score, SF-36v2 subscales, and NIS-LL total and component scores will be analyzed for subjects with a non-missing baseline and specified visit assessment (i.e., complete case analysis).

8.3. Interim Analyses and Data Monitoring

8.3.1. Interim Analysis

No interim analyses are planned for this study.

8.3.2. Safety Monitoring Committee

An independent Safety Monitoring Committee (SMC), consisting of at least 2 clinicians and a biostatistician not directly involved with the conduct of the trial, will meet to review specified blinded subject data during the conduct of the study. The purpose of these independent data reviews is to assess the totality of the safety data and provide a recommendation to the Sponsor for continuation of dosing or protocol modifications.

There are 4 planned data review meetings and they are as follows:

- After the 20th subject reaches Month 3-Day 1
- After the 60th subject reaches the Month 3-Day 1 visit
- After the last enrolled subject reaches Month 3-Day 1
- After the last enrolled subject reaches Month 9-Day 1

A non-scheduled meeting may be called at the discretion of the Chairperson or the request of the Sponsor. The purpose of these independent data review is to assess the totality of the safety data and provide recommendations to the Sponsor for continuation of dosing or protocol study modifications. Details are provided in the SMC Charter.

8.4. Multicenter Studies

The randomization is not stratified by site. Likewise, analyses of efficacy data will not be stratified by study site. The number and percentage of subjects randomized by geographical region and study site will be summarized by treatment group and for all subjects.

8.5. Use of an “Efficacy Subset” of Patients

The Renal Evaluable Population will include subjects who had renal involvement, i.e., proteinuria $>0.5\text{g}/24$ hours (measured by 24-hour urine total protein excretion), at baseline and at least one post-baseline assessment of proteinuria.

The Peripheral Neuropathy Evaluable Population will include subjects who had peripheral nerve involvement at baseline (only if the subject had ascending sensorimotor neuropathy due to AL amyloidosis etiologies at screening answered as yes) and had a baseline Neuropathy Impairment Score–Lower Limbs (NIS-LL) total score of 2 or greater and at least one post-baseline NIS-LL total score.

The Hepatic Evaluable Population will include subjects who had hepatic involvement defined as $>1.5 \times \text{ULN}$ alkaline phosphatase at baseline and at least one post-baseline assessment of alkaline phosphatase.

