8.1 Analysis Populations

The Intent-to-Treat (ITT) Population will include all randomized subjects who receive any amount of study drug (NEOD001 or placebo). The ITT Population will be the primary population used for efficacy analyses. Treatment assignment will be based on the randomized treatment.

The Safety Population will include all subjects who receive any amount of study drug (NEOD001 or placebo). The Safety Population will be the primary population used for safety analyses. Treatment assignment will be based on the randomized treatment.

Efficacy Subset Populations:

The Renal Evaluable Population will include subjects who had renal involvement, i.e., proteinuria >0.5 g/24 hours (measured by 24-hour urine total protein excretion), at baseline and at least one postbaseline assessment of proteinuria.

The Peripheral Neuropathy Evaluable Population will include subjects who had peripheral nerve involvement at baseline (only if the subject had ascending sensorimotor neuropathy due to AL amyloidosis etiologies answered as yes) and had a baseline Neuropathy Impairment Score–Lower Limbs (NIS-LL) total score of 2 or greater and at least one postbaseline NIS-LL total score.

The Hepatic Evaluable Population will include subjects who had hepatic involvement defined as $>1.5 \times$ ULN alkaline phosphatase at baseline and at least one postbaseline assessment of alkaline phosphatase.

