8.2.2. Responder Endpoints

The primary analysis for best response analyses will consider a subject as a non-responder until a response is achieved.

For other categorical efficacy endpoints in which subjects are classified as either a responder or a non-responder (binary outcome) based on dichotomizing a continuous variable at each visit, analyses will use “observed cases,” where subjects who do not provide an assessment at the specified time point for the defining of response will not be included. That is, for the percentage of responders, the subject will not be included in the numerator or the denominator. To assess the effect of missing data as a sensitivity analyses, any subject who does not provide an assessment at the specified time point for the response definition will be considered as a non-responder, regardless of treatment group. For analyses using a 3-category response (response, stable, progression), any subject who does not provide an assessment at the specified time point for the defining of response will be considered to have progressed, regardless of treatment group.

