8.2.3. Parametric Analyses

8.2.3.1. Missing Not at Random (MNAR): Imputation for Deaths

For the primary analysis of the SF-36v2 PCS score and NIS-LL total score, subjects who missed the EEOS visit due to death will be imputed as the worst EEOS value in the total population. Sensitivity analyses will be conducted imputing subjects who missed the EEOS visit due to death as: Zero, i.e. no quality of life (SF-36); or 88 for NIS-LL, i.e. no neurological function.

Exploratory analyses at other visits (i.e. not the EEOS visit) will use the same imputation methodology for time points at which no value is observed.

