8.9. Additional Secondary Efficacy Analysis

8.9.1. Renal Evaluable Subjects: Renal Best Response

The estimand for renal best response is the difference in renal best response rate between treatment groups through 12 months of treatment in all randomized subjects with AL amyloidosis and renal involvement (Section 8.5) who received any amount of drug.

The secondary efficacy analysis will test the following hypotheses:

- H_0 : The percentage of renal best response through 12 months of treatment is equal between placebo and NEOD001.
- H_1 : The percentage of renal best response through 12 months of treatment is different between placebo and NEOD001.

All visits after the first infusion of study drug up to and through the EEOS visit will be used to evaluate 12 months of treatment. Best renal response will be analyzed in the same manner described in Section 8.7 for the primary efficacy endpoint.

If an assessment qualifies as both response and progression (see Section 2.3.3.1), then assessments will be counted as progression for the primary analysis. A sensitivity analysis will be conducted counting an assessment that qualifies both as response and progression as a response.

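### The renal, neuropathy and hepatic evaluable populations require a post-baseline measurement that the estimands do not, so involved subjects lost before the first reading drop out of the analysis

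*SAP*

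**What the plan says.** SAP 8.5 defines three organ populations, each by a baseline criterion plus a later measurement:

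- **Renal:** proteinuria above 0.5 g/24 hours "at baseline and at least one post-baseline assessment of proteinuria".
- **Peripheral neuropathy:** nerve involvement at baseline with an NIS-LL "total score of 2 or greater and at least one post-baseline NIS-LL total score".
- **Hepatic:** more than 1.5 × ULN "alkaline phosphatase at baseline and at least one post-baseline assessment of alkaline phosphatase".

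SAP 2.3.3 repeats these conditions. Protocol 8.1 has them too; its renal set, for example, needs involvement "at baseline and at least one postbaseline assessment of proteinuria".

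The estimands are worded differently. SAP 8.9.1 targets the renal response difference "in all randomized subjects with AL amyloidosis and renal involvement (Section 8.5) who received any amount of drug". SAP 8.9.2 and 8.9.3 use parallel wording for neuropathy and hepatic involvement.

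The missing-data rules that apply inside these sets are:

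- **SAP 8.2.2 (renal and hepatic best response):** the primary analysis "will consider a subject as a non-responder until a response is achieved".
- **SAP 8.2.3.1 (NIS-LL, deaths):** "subjects who missed the EEOS visit due to death will be imputed as the worst EEOS value in the total population".
- **SAP 8.2.3.2 (NIS-LL, other reasons):** multiple imputation under MAR, from a model that includes the strata and the baseline value.

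**The concern.** Whether a subject has renal, nerve or hepatic involvement is known before the first infusion. The later measurement does not help to identify involvement. Its only effect is to select subjects on what happens after randomization.

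The subjects it removes are those for whom the SAP has already chosen a handling rule, but they never enter the set in which the rule operates. For NIS-LL the result is uneven: a subject assessed at Month 3 who dies at Month 5 receives the worst value, while a subject who dies at week 6 with no reading is left out.

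If early loss differs between arms, the comparison on these endpoints is shifted, and the result no longer estimates the quantity stated in SAP 8.9. No planned sensitivity analysis restores the excluded subjects.

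**Working it through.** **The plan's own figures.** No sample size, power or expected loss is stated for the organ subsets, so there is no subset figure to reproduce. The only power statement concerns the primary endpoint: 50% against 22.5%, two-sided 0.05, 91% at about 130 subjects. A pooled-variance normal approximation without continuity correction gives 91.3% at 65 per arm, so that figure reproduces. It is unaffected here, because the primary analysis uses the ITT Population with no post-baseline condition.

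**Who is exposed.**

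| Measure | First scheduled post-baseline reading (Schedule of Assessments; SAP Tables 3 and 4) | Earlier chance to be measured |
|---|---|---|
| 24-hour urine protein | Month 3, target Day 56 | ETD or unscheduled visit |
| NIS-LL | Month 3, target Day 56 | ETD or unscheduled visit |
| ALP (chemistry) | Month 2, target Day 28, then monthly | ETD or unscheduled visit |

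Protocol 6.2 collects all three at the ETD visit, so stopping drug early does not by itself remove a subject. Those removed die, or leave without an ETD or unscheduled assessment, before the first reading.

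**What happens to them, side by side.**

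| Subject with baseline involvement and no post-baseline reading | Under the 8.5 definition | Under the 8.9 estimand and 8.2 rules |
|---|---|---|
| Renal or hepatic, any reason | Excluded | Non-responder (8.2.2) |
| NIS-LL, died | Excluded | Worst EEOS value (8.2.3.1) |
| NIS-LL, other reason | Excluded | Multiple imputation (8.2.3.2) |

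**Size, renal, one subject.** Assume 30 involved subjects in an arm and 12 responders. With everyone counted the rate is 12/30 = 40.0%. With one early non-responder dropped it is 12/29 = 41.4%, a rise of 1.4 percentage points.

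**Size, renal, unequal loss.** Scale from the Phase 1/2 study in Protocol 1.3.2, where 36 of 69 subjects were renal evaluable: 65 × 36/69 = 33.9, say 34 per arm. Assume 17 responders in each arm, so the true difference is zero (17/34 = 50.0% in both).

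- Loss 3 against 0: 17/31 = 54.8% against 50.0%, a spurious 4.8 points.
- Loss 5 against 0: 17/29 = 58.6% against 50.0%, a spurious 8.6 points. This needs 5/34 = 14.7% of one arm gone before any reading and nobody in the other, so it is an extreme case.
- Loss 3 against 3: 54.8% in both arms. There is no spurious difference, but both rates are inflated.

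**Direction.** Dropping a renal or hepatic non-responder raises that arm's rate. Dropping an NIS-LL death removes a worst value and makes the arm look better. For an NIS-LL withdrawal for another reason, the imputed value could lie on either side of the arm mean, so the direction is not fixed.

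**The case against.** **The estimands point to Section 8.5, and SAP section 8 declares these subsets an exception to the ITT Population.** On that reading the post-baseline condition is part of the estimand, prespecified and the same in both documents. The exception does justify restricting to subjects with organ involvement. It does not turn a statement about all randomized subjects who received any drug into one about those who were later measured. The reference is attached to the word involvement, which 8.5 fixes at baseline.

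**Missing-data rules work within a population and do not define it.** This is correct: 8.2.2 and 8.2.3 are cut short by 8.5 rather than contradicted by it. The mismatch that remains is between 8.5 and the estimands.

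**The exposed group is small.** This stands. ETD visits keep most early discontinuers in, monthly ALP means that the hepatic set should lose very few, and no early-loss rate is given from which a material bias could be shown.

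**Stronger readings that the documents do not support.**

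- A reader might infer that the worst-value rule for deaths is defeated in all three sets. Among these endpoints it covers NIS-LL only.
- A reader might set an NIS-LL shift against the 2-point progression criterion. With 10 other subjects averaging zero change and an assumed death value of +15 to +30, the raw arm mean moves by 15/11 = 1.4 to 30/11 = 2.7 points. But those inputs are assumptions, the planned estimate is an adjusted MMRM mean, and the 2-point criterion classifies individual subjects. The comparison is not valid.
- A reader might conclude that every lost subject is a worst outcome. For NIS-LL that holds for deaths only.

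**Conclusion.** The mismatch is real and should be corrected. Membership of all three organ sets depends on a post-randomization measurement, while the estimands are stated for all randomized, dosed subjects with baseline involvement. The existing rules for non-response, death and other missing data therefore do not reach the earliest losses.

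The likely effect is modest: about 1.4 percentage points per dropped renal non-responder under the assumed 12 of 30, and less concern for the hepatic endpoint. Larger distortions need a marked imbalance in early loss, which nothing in the documents predicts. Subset sizes, responder counts and loss counts are all assumptions here.

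The affected endpoints are additional secondary endpoints outside the fixed testing sequence in SAP 8.6. A reader should not infer that the primary or key secondary conclusions are at risk; their estimands and analyses carry no such condition.

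**What to change.** Before unblinding:

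1. In SAP 8.5 and 2.3.3, define each organ population by its baseline involvement criterion plus receipt of any study drug, and remove the post-baseline requirement.
2. Count renal and hepatic subjects with no post-baseline reading as non-responders under 8.2.2.
3. Handle NIS-LL subjects with no post-baseline reading through 8.2.3: worst value after death, multiple imputation otherwise. The imputation model already contains strata and baseline, so no new method is needed.
4. Keep the present evaluable sets as a sensitivity analysis.
5. Record the departure from Protocol 8.1 in SAP section 10, as is already done for the Safety Population. No protocol amendment is needed.

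The cost is some SAP wording and one more population flag. Renal and hepatic response rates may be slightly lower, because a few more non-responders enter the denominator.
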